11.2. Appendix 2: Clinical Laboratory Tests

- The tests detailed in [Table 5](#) will be performed by the local laboratory.
- Protocol-specific requirements for inclusion or exclusion of participants are detailed in [Section 5](#) of the protocol.
- Additional tests may be performed at any time during the study as determined necessary by the investigator or required by local regulations.
- Protocol-specific requirements for inclusion or exclusion of participants are detailed in [Section 5](#) of the protocol.
- Additional tests may be performed at any time during the study as determined necessary by the investigator or required by local regulations.
- Pregnancy Testing
- Refer to [Section 5.1](#) Inclusion Criteria for screening pregnancy criteria.
- Pregnancy testing (urine or serum as required by local regulations) should be conducted at per the SoA during intervention
- Additional serum or urine pregnancy tests may be performed, as determined necessary by the investigator or required by local regulation, to establish the absence of pregnancy at any time during the participant's participation in the study.
- Testing for SARS-CoV-2 as per protocol should be undertaken using PCR laboratory testing. Sponsor approval is required for the use of non-PCR based tests for SARS-CoV-2 in the protocol.

Table 5 Protocol-Required Safety Laboratory Assessments

Laboratory Assessments	Parameters			
Haematology	Platelet Count	RBC Indices: MCV MCH %Reticulocytes		WBC count with Differential: Neutrophils Lymphocytes Monocytes Eosinophils Basophils
	RBC Count			
	Haemoglobin			
	Haematocrit			
Clinical Chemistry ¹	BUN	Potassium	Aspartate Aminotransferase (AST)/ Serum Glutamic-Oxaloacetic Transaminase (SGOT)	Total and direct bilirubin
	Creatinine	Sodium	Alanine Aminotransferase (ALT)/ Serum Glutamic-Pyruvic Transaminase (SGPT)	Total Protein
	Glucose fasting	Calcium	Alkaline phosphatase	CPK
Coagulation tests	PT	PTT	INR	Coagulation tests
Routine Urinalysis	
 • Specific gravity • pH, glucose, protein, blood, ketones, bilirubin, urobilinogen, nitrite, leukocyte esterase by dipstick • Microscopic examination (if blood or protein is abnormal) 			

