4. Record the date/time of the PK blood sample draw and the date/time of the last dose of study intervention prior to PK blood sample draw on the CRF. If the date or time of the last dose is unclear, provide the participant's best approximation. If the date/time of the last dose cannot be approximated OR a PK sample cannot be collected in the time period indicated above, do not obtain a PK sample. Instructions for sample handling and shipping are in the SRM.

References

11.7. Appendix 7: Division of AIDS Table for Grading the Severity of Adult and Paediatric Adverse Events Version 2.1, March 2017

The Division of AIDS Table for Grading the Severity of Adult and Pediatric Adverse Events (“DAIDS AE Grading Table”) is a descriptive terminology which can be utilised for Adverse Event (AE) reporting. A grading (severity) scale is provided for each AE term.

The table can be found at:

<https://rsc.niaid.nih.gov/sites/default/files/daidsgradingcorrectedv21.pdf> (accessed 6 April 2020)

The severity of injection site erythema/redness and swelling/induration will be graded based on surface area (and other symptoms) according to DAIDS.

Reference

U.S. Department of Health and Human Services, National Institutes of Health, National Institute of Allergy and Infectious Diseases, Division of AIDS. Division of AIDS (DAIDS) Table for Grading the Severity of Adult and Pediatric Adverse Events, Version 2.1. [March 2017]. Available from:
<https://rsc.tech-res.com/docs/default-source/safety/daids-ac-grading-table-mar2017.pdf>

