10.8. Appendix 8: Values of Potential Clinical Importance

10.8.1. Laboratory Values and Site Reactions to Injections and Infusions

Laboratory values and site reactions to injections and infusions will be graded based on the Division of AIDS Table for Grading the Severity of Adult and Pediatric Adverse Events Version 2.1, July 2017, as specified in the protocol Appendix 11.7, and shown below. Only numeric portion will be used, and higher grade will be assigned if the same criteria is applied to multiple grades.

HEMATOLOGY				
	Grade 1	Grade 2	Grade 3	Grade 4
Absolute Lymphocyte Count, Low (cell/mm ³ ; cells/L) > 5 years of age (not HIV infected)	600 to < 650 0.600 × 10 ⁹ to < 0.650 × 10 ⁹	500 to < 600 0.500 × 10 ⁹ to < 0.600 × 10 ⁹	350 to < 500 0.350 × 10 ⁹ to < 0.500 × 10 ⁹	< 350 < 0.350 × 10 ⁹
Absolute Neutrophil Count, Low (cells/mm ³ ; cells/L) > 7 days of age	800 to 1,000 0.800 × 10 ⁹ to 1.000 × 10 ⁹	600 to 799 0.600 × 10 ⁹ to 0.799 × 10 ⁹	400 to 599 0.400 × 10 ⁹ to 0.599 × 10 ⁹	< 400 < 0.400 × 10 ⁹
Hemoglobin, Low (g/dL; mmol/L) ≥ 13 years of age (male only)	10.0 to 10.9 6.19 to 6.76	9.0 to < 10.0 5.57 to < 6.19	7.0 to < 9.0 4.34 to < 5.57	< 7.0 < 4.34
Hemoglobin, Low (g/dL; mmol/L) ≥ 13 years of age (female only)	9.5 to 10.4 5.88 to 6.48	8.5 to < 9.5 5.25 to < 5.88	6.5 to < 8.5 4.03 to < 5.25	< 6.5 < 4.03
Platelets, Decreased (cells/mm ³ ; cells/L)	100,000 to < 125,000 100.000 × 10 ⁹ to < 125.000 × 10 ⁹	50,000 to < 100,000 50.000 × 10 ⁹ to < 100.000 × 10 ⁹	25,000 to < 50,000 25.000 × 10 ⁹ to < 50.000 × 10 ⁹	< 25,000 < 25.000 × 10 ⁹
White Blood Cell, Decreased (cells/mm ³ ; cells/L) > 7 days of age	2,000 to 2,499 2.000 × 10 ⁹ to 2.499 × 10 ⁹	1,500 to 1,999 1.500 × 10 ⁹ to 1.999 × 10 ⁹	1,000 to 1,499 1.000 × 10 ⁹ to 1.499 × 10 ⁹	< 1,000 < 1.000 × 10 ⁹

Coagulation				
	Grade 1	Grade 2	Grade 3	Grade 4
INR, High	1.1 to < 1.5 × ULN	1.5 to < 2.0 × ULN	2.0 to < 3.0 × ULN	≥ 3.0 × ULN
PTT, High	1.1 to < 1.66 × ULN	1.66 to < 2.33 × ULN	2.33 to < 3.00 × ULN	≥ 3.00 × ULN
PT, High	1.1 to < 1.25 × ULN	1.25 to < 1.50 × ULN	1.50 to < 3.00 × ULN	≥ 3.00 × ULN

Clinical Chemistry				
	Grade 1	Grade 2	Grade 3	Grade 4
Alkaline Phosphatase, High	1.25 to < 2.5 × ULN	2.5 to < 5.0 × ULN	5.0 to < 10.0 × ULN	≥ 10.0 × ULN
Alanine Aminotransferase, High	1.25 to < 2.5 × ULN	2.5 to < 5.0 × ULN	5.0 to < 10.0 × ULN	≥ 10.0 ULN
Aspartate Aminotransferase, High	1.25 to < 2.5 × ULN	2.5 to < 5.0 × ULN	5.0 to < 10.0 × ULN	≥ 10.0 × ULN

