Direct Bilirubin, High > 28 days of age	NA	NA	> ULN with other signs and symptoms of hepatotoxicity	> ULN with life-threatening consequences (e.g., signs and symptoms of liver failure)
Total Bilirubin, High > 28 days of age	1.1 to < 1.6 × ULN	1.6 to < 2.6 × ULN	2.6 to < 5.0 × ULN	≥ 5.0 × ULN
Calcium, High (mg/dL; mmol/L) ≥ 7 days of age	10.6 to < 11.5 2.65 to < 2.88	11.5 to < 12.5 2.88 to < 3.13	12.5 to < 13.5 3.13 to < 3.38	≥ 13.5 ≥ 3.38
Calcium, Low (mg/dL; mmol/L) ≥ 7 days of age	7.8 to < 8.4 1.95 to < 2.10	7.0 to < 7.8 1.75 to < 1.95	6.1 to < 7.0 1.53 to < 1.75	< 6.1 < 1.53
Creatine Kinase, High	3 to < 6 × ULN	6 to < 10 × ULN	10 to < 20 × ULN	≥ 20 × ULN
Creatinine, High Choose the method that selects for the higher grade	1.1 to 1.3 × ULN	> 1.3 to 1.8 × ULN OR Increase to 1.3 to < 1.5 × participant's baseline	> 1.8 to < 3.5 × ULN OR Increase to 1.5 to < 2.0 × participant's baseline	≥ 3.5 × ULN OR Increase of ≥ 2.0 × participant's baseline
Glucose Fasting, High (mg/dL; mmol/L)	110 to 125 6.11 to < 6.95	> 125 to 250 6.95 to < 13.89	> 250 to 500 13.89 to < 27.75	≥ 500 ≥ 27.75
Glucose, Low (mg/dL; mmol/L) ≥ 1 month of age	55 to 64 3.05 to < 3.55	40 to < 55 2.22 to < 3.05	30 to < 40 1.67 to < 2.22	< 30 < 1.67
Potassium, High (mEq/L; mmol/L)	5.6 to < 6.0 5.6 to < 6.0	6.0 to < 6.5 6.0 to < 6.5	6.5 to < 7.0 6.5 to < 7.0	≥ 7.0 ≥ 7.0
Potassium, Low (mEq/L; mmol/L)	3.0 to < 3.4 3.0 to < 3.4	2.5 to < 3.0 2.5 to < 3.0	2.0 to < 2.5 2.0 to < 2.5	< 2.0 < 2.0
Sodium, High (mEq/L; mmol/L)	146 to < 150 146 to < 150	150 to < 154 150 to < 154	154 to < 160 154 to < 160	≥ 160 ≥ 160
Sodium, Low (mEq/L; mmol/L)	130 to < 135 130 to < 135	125 to < 130 125 to < 130	121 to < 125 121 to < 125	≤ 120 ≤ 120

Site Reactions to Injections and Infusions				
	Grade 1	Grade 2	Grade 3	Grade 4
Injection Site Erythema or Redness > 15 years of age	2.5 to < 5 cm in diameter OR 6.25 to < 25 cm ² surface area	≥ 5 to < 10 cm in diameter OR ≥ 25 to < 100 cm ² surface area	≥ 10 cm in diameter OR ≥ 100 cm ² surface area	-
Injection Site Induration or Swelling > 15 years of age	2.5 to < 5 cm in diameter OR	≥ 5 to < 10 cm in diameter OR ≥ 25 to < 100	≥ 10 cm in diameter OR ≥	-

	6.25 to < 25 cm ² surface area	cm ² surface area	100 cm ² surface area	
--	--	---------------------------------	-------------------------------------	--

NA=not applicable; LLN = lower limit of normal; ULN=upper limit of normal.

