2.9.	Safety	AE5B	Summary of Adverse Events by System Organ Class and Preferred Term and Maximum Grade – Part 1 & Part 2	Include pooled treatment groups by dose & route	Cohort 1-5 IA Cohort 1-4, Cohort 1-5, EOS
2.10.	Safety	AE5B	Summary of Drug-Related Adverse Events by System Organ Class and Preferred Term and Maximum Grade – Part 1 & Part 2	Include pooled treatment groups by dose & route	Cohort 1-5 IA Cohort 1-4, Cohort 1-5, EOS
2.11.	Safety	ESI1	Summary of Characteristics of Seizures		Cohort 1-5, EOS
COVID-19 Assessment					
2.12.	Safety	PAN1	Summary of COVID-19 Assessments for Subjects with COVID-19 Adverse Events – Part 1 & Part 2		Cohort 1-5, EOS
2.13.	Safety	PAN2	Summary of COVID-19 Additional Assessments for Subjects with COVID-19 Adverse Events – Part 1 & Part 2		Cohort 1-5, EOS
2.14.	Safety	PAN3	Summary of COVID-19 Symptoms for Subjects with COVID-19 Adverse Events – Part 1 & Part 2		Cohort 1-5, EOS

CONFIDENTIAL

212482

Safety: Tables					
No.	Population	GSK Standard/ Example Shell	Title	Programming Notes	Deliverable [Priority]
2.15.	Safety	PAN4	Summary of COVID-19 Pandemic Visit Impacts – Part 1 & Part 2		Cohort 1-5, EOS
Laboratory: Chemistry					
2.16.	Safety	LB1	Summary of Clinical Chemistry Values – Part 1 & Part 2		Cohort 1-5, EOS
2.17.	Safety	LB1	Summary of Clinical Chemistry Changes from Baseline – Part 1 & Part 2		Cohort 1-5, EOS
2.18.	Safety	LB16A	Summary of Clinical Chemistry Results by Maximum Grade Increase Post-Baseline Relative to Baseline – Part 1 & Part 2	Unscheduled visits are included for determining maximum grade	Cohort 1-5 IA Cohort 1-4, Cohort 1-5, EOS
Laboratory: Hematology					
2.19.	Safety	LB1	Summary of Hematology Values – Part 1 & Part 2		Cohort 1-5, EOS
2.20.	Safety	LB1	Summary of Hematology Changes from Baseline – Part 1 & Part 2		Cohort 1-5, EOS
2.21.	Safety	LB16A	Summary of Hematology Results by Maximum Grade Increase Post-Baseline Relative to Baseline – Part 1 & Part 2	Unscheduled visits are included for determining maximum grade	Cohort 1-5 IA Cohort 1-4, Cohort 1-5, EOS
Laboratory: Coagulation					
2.22.	Safety	LB1	Summary of Coagulation Values – Part 1 & Part 2		Cohort 1-5, EOS
2.23.	Safety	LB1	Summary of Coagulation Changes from Baseline – Part 1 & Part 2		Cohort 1-5, EOS
2.24.	Safety	LB16A	Summary of Coagulation Results by Maximum Grade Increase Post-Baseline Relative to Baseline – Part 1 & Part 2	Unscheduled visits are included for determining maximum grade	Cohort 1-5, EOS
ECG					

Safety: Tables					

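### The grading rule in SAP 10.8.1 makes any post-baseline rise of direct bilirubin above ULN a Grade 4 in Table 2.18

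*SAP*

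**What the plan says.** SAP 10.8.1 adopts the DAIDS grading table named in Protocol Appendix 7 and adds a programming convention: "Only numeric portion will be used, and higher grade will be assigned if the same criteria is applied to multiple grades".

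The direct bilirubin row of the SAP's clinical chemistry table reads:

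- Grades 1 and 2: NA, which the table's key expands as "NA=not applicable".
- Grade 3: "> ULN with other signs and symptoms of hepatotoxicity".
- Grade 4: "> ULN with life-threatening consequences (e.g., signs and symptoms of liver failure".

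Protocol Appendix 2 (Table 5) lists "Total and direct bilirubin" in the required clinical chemistry panel, so the analyte is measured at every scheduled chemistry draw.

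The grades are summarised in SAP Table 2.18, "Summary of Clinical Chemistry Results by Maximum Grade Increase Post-Baseline Relative to Baseline". It is scheduled for the Cohort 1-5 IA, Cohort 1-4, Cohort 1-5 and EOS deliverables, and unscheduled visits count towards the maximum grade.

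Protocol Appendix 7 describes the DAIDS table with the words "A grading (severity) scale is provided for each AE term" and states no numeric-only convention.

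**The concern.** For direct bilirubin, the clinical wording is all that separates Grade 3 from Grade 4, and all that separates either grade from a trivial excursion above ULN. Once it is removed, the two grades have the same criterion and the tie clause picks the higher. A small, isolated and symptom-free value is then tabulated in the grade that DAIDS reserves for life-threatening consequences.

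The place matters. Liver biochemistry abnormalities are a secondary endpoint (Protocol section 3), and drug-induced liver injury is a named risk (Protocol 2.3.1). Arms are small: Cohorts 1 to 4 each plan 18 participants on the 400 mg/mL formulation, so one misgraded participant is 1/18 = 5.6% of an arm. SAP 3.1 and 3.2 say that the Cohort 1-4 and Cohort 1-5 preliminary analyses exist to support a conference abstract and timely dissemination. The misgraded row could therefore reach readers before the full report.

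**Working it through.** The plan states no figure to reproduce. The check applies the SAP's rule to the SAP's own table.

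**Step 1. Strip the text from the direct bilirubin row.** Grade 1: none. Grade 2: none. Grade 3: > ULN. Grade 4: > ULN.

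**Step 2. Apply the tie clause.** Assigned grade = the highest grade whose numeric criterion is met.

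**Step 3. Compare with total bilirubin.** Its thresholds in the same SAP table are Grade 1 from 1.1, Grade 2 from 1.6, Grade 3 from 2.6 and Grade 4 from 5.0 x ULN.

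| Value (x ULN) | Direct bilirubin: grades met | Direct bilirubin: assigned | Total bilirubin: assigned |
|---|---|---|---|
| 0.9 | none | ungraded | ungraded |
| 1.0 | none | ungraded | ungraded |
| 1.01 | 3 and 4 | Grade 4 | ungraded |
| 1.1 | 3 and 4 | Grade 4 | Grade 1 |
| 1.5 | 3 and 4 | Grade 4 | Grade 1 |
| 2 | 3 and 4 | Grade 4 | Grade 2 |
| 5 | 3 and 4 | Grade 4 | Grade 4 |

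Direct bilirubin goes from ungraded to Grade 4 at ULN with nothing in between.

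**Step 4. Is another row affected in the same way?** Among the rows shown, direct bilirubin is the only one whose whole numeric criterion is identical in two grades. Fasting glucose overlaps at the single value 500 mg/dL (Grade 3 runs up to 500, Grade 4 starts at 500), where taking the higher grade does little harm. Creatinine carries its own instruction for choosing between methods.

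**Step 5. Is there an exemption?** The direct bilirubin row has no footnote, and the programming note for Table 2.18 deals only with unscheduled visits.

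**Step 6. Who shows up in Table 2.18?** The table counts increases from baseline, and SAP 5.2 defines a separate baseline for each phase. A participant at or below ULN at the phase baseline who later exceeds it moves from ungraded to Grade 4. A participant already above ULN at that baseline is Grade 4 there and shows no increase.

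**The case against.** The case for leaving the rule alone has four parts.

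- *It is open and conservative.* The rule is pre-specified and over-grades rather than hides. It touches one analyte in a Phase 1 study with no formal hypothesis, and the primary PK analysis is unaffected. All of this stands, and it limits the weight of the point. It does not make the grade correct.
- *Laboratory grades are not events.* Protocol 11.3.1 makes a laboratory finding an AE only if the investigator judges it clinically significant. Protocol 11.3.3 says an asymptomatic Grade 4 laboratory value needs clinical correlation before it is considered serious. This stands: Table 2.18 would show misgraded laboratory values, not false hepatic events.
- *Other displays reveal the truth.* Tables 2.16 and 2.17 give chemistry values and changes, Tables 2.33 and 2.34 cover liver stopping events and hepatobiliary abnormalities, and Listing 26 shows all chemistry data for participants with any toxicity. This stands only in part. Of these, only Table 2.33 is scheduled for the Cohort 1-5 IA and Cohort 1-4 deliverables; the others come with Cohort 1-5 and EOS.
- *Protocol decisions do not use this rule.* A reader might infer that false Grade 4 values would count towards the 25% pausing criterion in Protocol 7.1, which refers to Grade 3 or higher laboratory abnormalities. The documents do not support that. The numeric-only sentence appears only in the SAP, while Protocol Appendix 7 refers to DAIDS itself. The pausing text includes a judgement of relatedness by investigator and sponsor. SAP 3.1 limits the formal displays to the Cohort 1-4, Cohort 1-5 and CSR analyses, so Table 2.18 is not shown to feed the study team's safety reviews.

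**Conclusion.** The rule is wrong as written for this one analyte. Any direct bilirubin that crosses ULN after baseline is tabulated as Grade 4 in all four deliverables, however small the excess and whatever the symptoms. This follows from the SAP's rule and table without any further assumption. It is a reporting error in a liver-safety display and nothing wider.

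Two further inferences should be resisted.

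- *Eligibility.* A reader might infer that admitting Gilbert's syndrome, or isolated bilirubin above 1.5 x ULN, ensures many such cases. Protocol 5.2 accepts isolated bilirubin above that limit only when bilirubin is fractionated and direct bilirubin is below 35%. That caps the direct fraction and does not establish direct bilirubin above ULN. Anyone who does enter above ULN and is still above it at the phase baseline shows no increase.
- *Counts.* A reader might estimate how many participants are affected. Assuming that 2.5% of healthy samples exceed ULN and that there are 10 to 15 draws each, the share runs from 2.5% (draws fully correlated) to 1 - 0.975^10 = 22.4% or 1 - 0.975^15 = 31.6% (draws independent). The 2.5% rate is not in the documents, the range is very wide, and phase baselines are ignored. No count is claimed here.

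**What to change.** Add one sentence to SAP 10.8.1, for example: *Direct bilirubin is exempt from numeric-only grading; it is summarised as above ULN (yes/no) without a DAIDS grade, and graded bilirubin summaries use total bilirubin.*

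In Table 2.18, drop the graded direct bilirubin row and show the yes/no count in the chemistry tables instead. The tie clause can stay for the remaining analytes.

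The cost is the sentence and one programming exception. No data collection, protocol procedure or other display has to change.

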10.8.2. ECG

ECG Parameter	Units	Clinical Concern Range	
		Lower	Upper
Absolute			
Absolute QTc Interval	msec		>450
Absolute PR interval	msec	<120	>220
Absolute QRS Interval	msec	<75	>120
Change from Baseline			
Increase from Baseline QTc	msec		>60

10.8.3. Vital Signs

Vital Sign Parameter (Absolute)	Units	Clinical Concern Range	
		Lower	Upper
Systolic Blood Pressure	mmHg	<85	>140
Diastolic Blood Pressure	mmHg	<45	>90
Heart Rate (Males)	bpm	<45	>100
Heart Rate (Females)	bpm	<50	>100

10.9. Appendix 9: Abbreviations & Trademarks

10.9.1. Abbreviations

Abbreviation	Description
AC	Active Control
ADaM	Analysis Data Model
AE	Adverse Event
ANOVA	Analysis of Variance
AUC	Area under Concentration-Time Curve
AUC0-t	AUC for each Injected Dose from Time Zero to Last Quantifiable Time Point or 4 Weeks Following the Injection, whichever is earlier
BMI	Body Mass Index
CAB	Cabotegravir
CDISC	Clinical Data Interchange Standards Consortium
CI	Confidence Interval
C _{max}	Maximum Observed Plasma Concentration
CSR	Clinical Study Report
C _τ	Trough Concentrations at 4 Weeks Following First Injection (or Earlier If The Second Injection Occurs at <4-Week Interval) and 4 Weeks Following The Second Injection
DBF	Database Freeze
DBR	Database Release
DP	Decimal Place
DVM	Data Validation Manual
eCRF	Electronic Case Report Form
CV	Coefficient of Variation
CV _b	Between-Subject Geometric CV
ECG	Electrocardiogram
GSK	GlaxoSmithKline
IA	Interim Analysis
ICF	Informed Consent Form
IDSL	Integrated Data Standards Library
IG	Implementation Guide
IM	Intramuscular
ISR	Injection Site Reaction
K _{ALA}	Terminal Absorption Elimination Rate Constant
LLN	Lower Limit of Normal
NQ	Not Quantifiable Value
CCI	
OLI	Oral Lead-In
CCI	
PK	Pharmacokinetic
Q4W	Four-Weekly

Q12W	Twelve-Weekly
QD	Once Daily
QTcB	QT Duration Corrected for Heart Rate by Bazett's Formula
QTcF	QT Duration Corrected for Heart Rate by Fridericia's Formula
RAP	Reporting and Analysis Plan
REML	Restricted Maximum Likelihood
SAC	Statistical Analysis Complete
SAE	Serious Adverse Event
SAS	Statistical Analysis Software
SC	Subcutaneous
SD	Standard Deviation
SDL	Source Database Lock
SDTM	Study Data Tabulation Model
SMQ	Standardized MedDRA Query
SRT	Safety Review Team
STR	Study Team safety & PK Review
$t_{1/2}$	Terminal Absorption Elimination Half-Life
tmax	Time of Cmax
ULN	Upper Limit of Normal

10.9.2. Trademarks

Trademarks of the ViiV Healthcare Group of Companies

Trademarks not owned by the ViiV Healthcare Group of Companies
WinNonlin
SAS
NONMEM

10.10. Appendix 10: List of Data Displays

All data displays will use the term “subject” rather than “participant” in accordance with CDSIC and GSK Statistical Display Standards.

10.10.1. Data Display Numbering

The following numbering will be applied for RAP generated displays:

Section	Tables	Figures
Study Population	1.1 to 1.19	
Safety	2.1 to 2.70	2.1 to 2.4
Pharmacokinetic	3.1 to 3.12	3.1 to 3.12
Section	Listings	
ICH Listings	1 to 82	
Other Listings	68 to 75	

10.10.2. Mock Example Shell Referencing

Nonstandard specifications will be referenced as indicated and if required example mock-up displays provided in separate documents.

Section	Figure	Table	Listing
Study Population	POP_Fn	POP_Tn	POP_Ln
Safety	SAFE_Fn	SAFE_Tn	SAFE_Ln
Pharmacokinetic	PK_Fn	PK_Tn	PK_Ln

NOTES:

- Non-Standard displays are indicated in the ‘GSK Statistical Display Standard / Example Shell’ or ‘Programming Notes’ column as ‘[Non-Standard] + Reference.’

10.10.3. Deliverables

Delivery [Priority] ^[1]	Description
Cohort 1-5 IA	Preliminary Cohort 1-5 Interim Analysis: displays will exclude Cohort 4b data from participants who have received injection 1 but have not yet completed Injection 2 Day 1 or Follow-up Week 4 by the data analysis cut-off. Cohort 4b will remain blinded to the randomized mitigation treatments (topical steroids vs. NSAID) and results will not be presented by mitigation treatment.
Cohort 1-4	Cohort 1-4 Injection Phase Complete: when all participants in Part 1 Cohorts 1, 2, 3, 4 complete the 8-week Injection Phase.
Cohort 1-5	Injection Phase Complete: when all participants in Part 1 Cohorts 1, 2, 3, 4 and 4b complete the 8-week Injection Phase, all Cohort 4h participants complete the 4-week Injection Phase, and all participants in Part 2 complete the 24-week Injection Phase.

Delivery [Priority] ^[1]	Description
EOS	End of Study: when all participants complete the 52-week Follow-up Phase in Part 1 and Part 2.

NOTES:

1. Indicates priority (i.e. order) in which displays will be generated for the reporting effort

10.10.4. Study Population Tables

Study Population Tables					
No.	Population	GSK Standard / Example Shell	Title	Programming Notes	Deliverable [Priority]
Subject Disposition					
1.1.	Enrolled	NS1	Summary of Number of Subjects Enrolled – Part 1 & Part 2		Cohort 1-5, EOS
1.2.	Screened	ES6	Summary of Screening Status and Reasons for Screen Failures		Cohort 1-5, EOS
1.3.	Safety	ES1	Summary of Subject Disposition for the Subject Conclusion Record – Part 1 & Part 2		Cohort 1-5, EOS
1.4.	Safety	ES11	Summary of Outcome of Adverse Events which Led to Study Withdrawal at Each Study Period/Phase – Part 1 & Part 2		Cohort 1-5, EOS
1.5.	Safety	SD1	Summary of Treatment Status and Reasons for Discontinuation of Study Treatment – Part 1 & Part 2		Cohort 1-5, EOS
Protocol Deviations					
1.6.	Safety	DV1	Summary of Important Protocol Deviations – Part 1 & Part 2		Cohort 1-5 IA Cohort 1-4, Cohort 1-5, EOS
Population Analysed					
1.7.	Enrolled	SP1	Summary of Study Populations – Part 1 & Part 2		Cohort 1-5, EOS
Demographic and Baseline Characteristics					
1.8.	Safety	DM1	Summary of Demographic Characteristics – Part 1 & Part 2		Cohort 1-5 IA Cohort 1-4, Cohort 1-5, EOS
1.9.	Enrolled	DM11	Summary of Age Ranges – Part 1 & Part 2		Cohort 1-5, EOS
Exposure and Treatment Compliance					

Study Population Tables					
No.	Population	GSK Standard / Example Shell	Title	Programming Notes	Deliverable [Priority]
1.10.	Safety	EX5	Summary of Exposure to CAB – Part 1 & Part 2		Cohort 1-5, EOS

